6.2.2.2.5 Target lesion involves a bifurcation in which 2-vessel stenting is planned

6.2.2.2.6 Index procedure treatment plan for the target lesion includes stent overlapping

6.2.2.2.7 Index procedure treatment plan for the target vessel includes treatment of 2 target lesions that would result in 2 study stents placed <10 mm apart

6.2.2.2.8 Index procedure treatment plan for the target vessel includes vessel preparation other than balloon pre-dilatation (e.g., cutting balloon, atherectomy, thrombectomy, excimer laser angioplasty, brachytherapy)

6.2.2.2.9 Treatment plan includes repeat intervention (staged procedure)

### 6.3 Subject Screening

Patients requiring elective or urgent PCI will be pre-screened by a member of the research team who has received training on this Clinical Investigation Plan, including a review of the patient's medical history and any testing that has been performed as a part of the patient's routine medical care, to determine whether the patient meets general eligibility criteria (inclusion and exclusion) for participation in the trial.

Potentially eligible subjects will undergo the process of informed consent (§6.4) prior to the performance of any study-specific assessments. After informed consent has been obtained, screening / baseline tests and examinations will be performed to verify eligibility and to collect baseline study data. Assessments performed as part of standard medical care prior to study enrollment are valid sources of data for verifying study eligibility and collecting baseline study data, provided that the previously performed assessments comply with applicable protocol requirements. Potentially eligible subjects will be randomized to a treatment group and enrolled in the study only after it has been confirmed (at the time of the index procedure cardiac catheterization) that the patient meets all angiographic inclusion criteria and no angiographic exclusion criteria, and after treatment of any non-target lesion has been completed successfully without complication.

A screening log will be maintained to document the enrollment and subject number, or reason for non-enrollment of subjects screened but not enrolled in the study. Subjects who receive any study stent during the index procedure (BuMA DES or DP EES) must complete all assigned follow-up assessments (to 5 years); subjects who do not receive any study stent during the index procedure will be followed to 12 months only for safety.

### 6.4 Informed Consent

Relevant study information will be summarized on a Patient Information and Consent Form ("Informed Consent Form [ICF]") that has been approved by applicable regulatory authorities. This document, or a modification based on local IRB/EC recommendations, must be approved by the applicable IRB/EC and signed by each subject or his/her legal representative prior to the performance of any study-specific procedures or assessments.

Prior to obtaining informed consent, the investigator (or designee) should provide the relevant study information to the patient in both oral and written form, in a language and at a level of complexity understandable to the patient. Patients should not be coerced, persuaded, or unduly influenced to participate or remain in the trial. The patient or his/her legal representative must be given ample time and

opportunity to inquire about details of the trial, and all questions about the trial should be answered to the satisfaction of the patient or the representative.

The written informed consent form should be signed and personally dated by the subject or his/her legal representative, and by the person who conducted the informed consent discussion (investigator or designee), prior to the subject's participation in the trial. If the subject or his/her legal representative is unable to read the consent form, a witness should be present during the entire informed consent discussion. After the informed consent form is read to the subject and signed by the subject or his/her legal representative, the witness should also sign the consent form, attesting that informed consent was freely given by the subject or his/her legal representative. For non-English speaking subjects, the written informed consent should be translated into the subject's native language, or a short form (including the elements of informed consent translated into the subject's native language) should be used. The informed consent process should be documented in each subject's medical record.

The subject or his/her legal representative must be provided with a copy of the signed and dated informed consent form.

The Investigator shall inform the subject of any new significant findings occurring during the clinical investigation, including the need for additional medical care that may be required, that may be relevant to the subject and his/her willingness to continue participation in the study. The consent form should be updated or amended whenever such new information becomes available and updated consent shall be recorded.

## 6.5 Subject Enrollment

Potentially eligible subjects who meet all general inclusion criteria and no general exclusion criteria and who have consented to participate in the trial will undergo screening/baseline assessments. At the index procedure cardiac catheterization, the target lesion(s), target vessel(s), and index procedure treatment plan will be evaluated to confirm that all angiographic inclusion criteria (§6.2.1.2) and no angiographic exclusion criteria (§6.2.2.2) are met.

If the subject meets all inclusion and no exclusion criteria, and treatment of any non-target lesion has been completed successfully without complication, the subject will be randomized to a treatment arm (BuMA DES or DP EES in a 2:1 ratio) and enrolled in the trial. Randomization will be stratified by the presence of acute coronary syndrome (i.e., patients with stable angina or silent ischemia versus patients with unstable angina or non-ST segment elevation myocardial infarction), by diabetes status (i.e., subjects with vs. without medically-treated diabetes mellitus), as well as by study center. All target lesion(s) should be treated with the assigned stent type.

The point of enrollment is the moment of randomization. All enrolled subjects will be assigned a study-specific patient identification number via the database system.

No single site will be permitted to enroll more than 10% of the total number of subjects in the trial (i.e., no single site may enroll more than 163 subjects).

## 6.6 Withdrawal and Replacement of Subjects

Subjects can withdraw from the study at any time; the reason(s) for withdrawal (if given) will be documented. All data available at the time of withdrawal (if any) will be used for analysis, unless the subject has explicitly forbid the use of such data and has documented this preference in accordance with local regulatory requirements. With the exception of ascertainment of survival status (in accordance with applicable legal and ethical considerations), there will be no further follow-up (per this study protocol) on a subject who has withdrawn. Subjects who withdraw from the study will not be replaced. The withdrawal of a subject can be initiated by the Investigator if he/she determines it is in the best interest of the patient.

## 6.7 Protocol Deviations

All deviations from the requirements of this Clinical Investigation Plan will be considered protocol deviations. In the event of a protocol deviation, a Protocol Deviation form should be completed in the eCRF and submitted to the Sponsor and to the relevant regulatory body (if required by local regulations). Protocol deviations that will be collected include, but are not limited to:

- Failure to obtain informed consent, or failure to obtain informed consent prior to the performance of study-specific procedures or assessments
- Enrollment of a subject who did not meet all study inclusion criteria, or who met one or more study exclusion criteria
- Failure to complete protocol-specified assessments

A major protocol deviation is a protocol deviation that may affect the scientific soundness of the protocol or the rights, safety, or welfare of the patients. Major protocol deviations include, but are not limited to: failure to obtain informed consent, enrollment of a subject not meeting study eligibility criteria, and implantation of a study stent in a patient who has not reached the point of enrollment. Major protocol deviations require immediate reporting to the Study Monitor and the Institutional Review Board/Ethics Committee.

Site-level deviations are those that occur at the study center but are not directly related to a specific patient. The Sponsor reserves the right to terminate the study participation of a site with excessive protocol deviations, or to suspend the site's participation until an adequate system to reduce further deviations has been implemented.

## 7.0 Study Procedures and Assessments

### 7.1 Schedule of Procedures and Assessments

Table 3. Study Schedule of Procedures and Assessments

	Screening / Baseline	Index Procedure (day 0)	Post- procedure / Pre-discharge	30 days (30 ± 7 days)	6 months (± 30 days)	12 months (± 30 days)	2, 3, 4, 5 years (± 60 days)
	Clinic Visit	Clinic Visit	Clinic Visit	Clinic Visit	Telephone Contact / Clinic Visit	Clinic Visit / Telephone Contact 	Telephone Contact  / Clinic Visit
General eligibility criteria	•						
Informed consent	•						
Pregnancy test (if applicable)	• 						
Medical history	•						
Physical examination	•						
Anginal status	•		•	•	•	•	•
Concomitant medications	•	•	•	•	•	•	•
12-lead ECG 	•		•	•		• 	
Laboratory testing 	•		•	•		• 	
Cardiac biomarkers	• 		• 				
Coronary angiography 		•					
Angiographic eligibility criteria		•					
Stent implantation		•					
Adverse events 		•	•	•	•	•	•

 Female subjects of childbearing potential must have a pregnancy test (performed per site standard practice) within 7 days prior to the index procedure to confirm study eligibility.

 The screening/baseline ECG may be performed up to 21 days prior to procedure, except when there is evidence of acute or recent MI or UA, in which case the ECG must be performed within 24 hours prior to the index procedure. An ECG must also be performed within 24 hours post procedure or prior to hospital discharge (whichever occurs first) and at the 30-day and 12-month follow-up visits.

 Laboratory testing should be performed per site standard practice; if laboratory testing is part of the standard of care and includes CBC and serum creatinine, these should be recorded.

 The pre-procedure blood draw for cardiac biomarkers testing (preferably troponin [cTn] I or T; if not available, then CKMB is acceptable) may be performed within 48 hours prior to the index procedure, except when there is evidence of acute or recent (<7 days) MI or UA, in which case the draw must be performed within 24 hours prior to the index procedure. If the subject does not have a known diagnosis of acute MI or UA within 96 hours prior to the index procedure, assessment of cardiac biomarkers may be obtained after the start of the index procedure but prior to device implantation.

 Cardiac biomarkers (preferably cTn I or T; if not available, then CKMB is acceptable) should be measured 2 to 6 (up to 12) hours postprocedure. If cardiac biomarkers are elevated and there is a clinical suspicion of myocardial

ischemia (for example, due to new ischemic ECG changes [such as ischemic ST changes or new pathological Q waves] or new LBBB, angiographic evidence of a flow-limiting complication, or imaging evidence of new loss of viable myocardium or new regional wall motion abnormality), serial measurements should be taken every 6 to 12 hours until a decline is noted.

 Angiographic eligibility criteria must be confirmed at the time of the index procedure. All angiographic films for the index procedure and any repeat intervention or repeat diagnostic cardiac catheterization must be forwarded to the Angiographic Core Laboratory (§17.3).

 Procedural angiographic images, ECG data, and the results of laboratory testing should be submitted for all repeat revascularizations. For all adverse events that represent a potential endpoint event, all relevant medical information (including clinically relevant imaging data, ECG data, and the results of relevant laboratory testing performed as part of the standard of care) should be collected and retained as part of the research file to support adverse event analysis and adjudication.

 Subjects who do not receive a study stent during the index procedure will be followed to 12 months only.

 For the duration of the Coronavirus Disease 2019 (COVID-19) pandemic, phone follow-up or virtual visit at 12 months is permitted if necessary to assure the safety of trial participants. The reason for the conduct of the phone follow-up should be documented in the eCRF. Phone follow-ups conducted for other reasons (e.g., to collect all available data in a subject otherwise lost to follow-up) should continue to be recorded as protocol deviations, and details of the protocol deviation must be captured in the appropriate eCRF. Please refer to Section 7.7 for additional considerations related to alternate assessment methods.

 For subjects who underwent a phone follow-up at the 12-month time point for any reason, it is preferable that the 2-year follow-up be conducted as an in-clinic visit.

## 7.2 Screening / Baseline

The following tests and examinations must be performed prior to the procedure to verify eligibility and to collect baseline study data. Note that assessments performed as part of standard medical care prior to study enrollment are valid sources of data for verifying study eligibility and collecting baseline study data, provided that the previously performed assessments comply with applicable protocol requirements.

- Review of general inclusion and exclusion criteria.
- Female patients of childbearing potential must have a pregnancy test performed within 7 days prior to the procedure
- Relevant medical history and patient demographic information
- Physical examination
- Anginal status (CCS, Braunwald classification of unstable angina, or silent ischemia)
- Documentation of all concomitant medications
- A 12-lead electrocardiogram (ECG). The ECG may be performed up to 21 days prior to procedure, except when there is evidence of acute or recent MI or UA, in which case the ECG must be performed within 24 hours prior to the index procedure.

Laboratory testing per site standard practice; if laboratory testing is part of the standard of care and includes CBC and serum creatinine, these should be recorded. The results of any additional tests performed per site standard practice should also be collected.

- The blood draw for cardiac biomarkers testing (preferably cTn I or T; if not available, then CKMB is acceptable) may be performed within 48 hours prior to the index procedure, except when there is evidence of acute or recent (<7 days) MI or UA, in which case the draw must be performed within 24 hours prior to the index procedure. If the subject does not have a known diagnosis of acute MI or UA within 96 hours prior to the index procedure, assessment of cardiac biomarkers may be obtained after the start of the index procedure but prior to device implantation.

## 7.3 Index Procedure

### 7.3.1 Angiographic Imaging

The imaging protocol includes angiography pre-intervention, post-stent implantation, and after any post-dilatation (if any), in addition to documentation of any procedural complications. For details, please refer to the Angiographic Imaging Acquisition Guidelines (§17.3). All procedural angiographic imaging should be forwarded to the Angiographic Core Laboratory for analysis.

### 7.3.2 Eligibility Confirmation

At the time of the index procedure, the investigator should confirm the following before the patient is randomized to a treatment arm and enrolled in the trial:

- 1) The target vessel(s), target lesion(s), and treatment plan meet all angiographic inclusion criteria and no exclusion criteria; AND
- 2) Treatment of a non-target lesion (if performed) has been successfully completed without complications (see §7.3.3)

### 7.3.3 Treatment of Non-target Lesion

Treatment of a single non-target lesion that does not meet study angiographic eligibility criteria during the index procedure is permitted, provided that all the following conditions are met:

- 1) The non-target lesion is treated first, prior to randomization.
- 2) The non-target lesion is located in a separate epicardial vessel from the target lesion(s). The epicardial vessels are defined as the LAD, LCx, and RCA, each including its respective branches; e.g., a patient with a target lesion in the LAD would not be eligible for treatment of a non-target lesion in a diagonal branch. The ramus intermedius is considered a branch of the LCx.
- 3) The non-target lesion is treated with an approved (FDA-approved, CE-marked, or PMDA-approved, as applicable) commercially available device.
- 4) Treatment of the non-target lesion was successful, defined as:
  - a. Final % diameter stenosis (%DS)  $\leq$ 30% with final TIMI 3 flow AND
  - b. Without the following complications
    - i. Residual dissection (NHLBI grade  $\geq$  type B)
    - ii. Angiographic complications (e.g., distal embolization, side branch closure)
    - iii. Chest pain lasting > 5 minutes
    - iv. ST segment elevation or depression lasting > 5 minutes.

If all the above conditions have been met, the patient may be randomized to a treatment arm and enrolled in the trial. The non-target lesion will not be considered in the primary analyses.

### 7.3.4 Treatment of Target Lesion(s)

Implantation of the assigned study stent(s) in the designated target lesion(s) should be performed per site standard practice in accordance with each manufacturer's Instructions for Use. All target lesions should be treated with the assigned study stent type.

Pre-dilatation of the target lesion(s) with an appropriately sized angioplasty balloon is recommended, and should be documented on the eCRF.

The investigator should choose the appropriate diameter and length of the stent(s) to be implanted by visual estimate, ensuring that the selected stent length allows complete coverage of the target lesion with 1-2 mm of healthy vessel overlap at each end. If the stent is under-dilated following initial expansion, post-dilation should be performed with an appropriately sized balloon.

In the event of a need for a bailout device at the target lesion (e.g., edge dissection, unplanned additional device required to cover target lesion), the same device as the implanted device should be used (i.e., BuMA DES for BuMA DES-treated lesions, DP EES for DP EES-treated lesions), with 1-2 mm overlap of the bailout and implanted stents.

Procedural details should be entered into the eCRF. ACT should be measured at the onset of the procedure and at regular intervals throughout the procedure per routine hospital practice.

### 7.3.5 Unplanned Staged Procedures

Subjects with planned staged procedures are not eligible for enrollment in the study (refer to Angiographic Exclusion Criterion #9, §6.2.2.2.9). However, if index procedure complications (excessive contrast load or radiation exposure, blood loss, or patient intolerance) necessitate discontinuation of the procedure, staged treatment of a target lesion is permitted provided the staged procedure is performed >72 hours and <14 days after the index procedure. The same device as the previously implanted device(s) must be used (i.e., BuMA DES for BuMA DES-treated subjects, DP EES for DP EES-treated subjects).

### 7.3.6 Concomitant Medical Therapy

Dual antiplatelet therapy (DAPT) will be administered according to physician standard practice in accordance with published guidelines and local standards of care. Patients with stable ischemic heart disease will be required to receive DAPT for at least 6 months in the absence of contraindications; discontinuation of DAPT after 3 months is permitted (but not required) in patients with a high risk of bleeding. Patients with ACS will be required to receive DAPT for at least 12 months in the absence of contraindications; discontinuation of DAPT after 6 months is permitted (but not required) in patients with a high risk of bleeding.

The following doses are recommended:

- ASA 300 to 325 mg oral or 250 mg IV loading dose and ASA 75-100 mg maintenance dose indefinitely. NOTE: Aspirin loading is recommended regardless of whether or not the patient was receiving chronic aspirin therapy prior to the procedure.

AND

- Clopidogrel 600 mg loading dose before procedure and 75 mg daily maintenance dose OR prasugrel 60 mg loading dose and 10 mg daily OR ticagrelor 180 mg loading dose and 90 mg twice daily. NOTE: For patients receiving chronic clopidogrel therapy prior to the procedure, pre-procedure re-loading with clopidogrel (600 mg) is recommended. For patients receiving chronic prasugrel or ticagrelor therapy prior to the procedure, re-loading is at the discretion of the operator.

Recommended loading dose, loading dose timing, and maintenance dosage may vary based on physician's discretion and applicable regional clinical guidelines. Approved adjunctive therapies (e.g., GP IIb/IIIa inhibitors, cangrelor) may be used according to physician preference in accordance with local standards of care. Each site is encouraged to commit to a consistent antiplatelet regimen to be applied to all subjects enrolled in the trial, independent of treatment group.

Procedural anticoagulation therapy should be administered according to physician standard practice in accordance with published guidelines and local standards of care.

All medications administered, including the dose and timing, should be recorded in the patient's medical record and the CRF.

## 7.4 Post-procedure / Pre-discharge Follow-up

The procedure is complete once the last guiding catheter has been removed from the patient. Thereafter, if a guiding catheter is re-introduced, this is considered a repeat intervention, which must be documented.

The post-procedure follow-up must include:

- Anginal status (CCS, Braunwald classification of unstable angina, or silent ischemia)
- Current concomitant medications documentation. If DAPT has been interrupted or terminated the stop date (and resumption date, if applicable) and the reason for interruption/termination should be recorded.
- A 12-lead electrocardiogram (ECG), to be completed within 24 hours post-procedure or prior to hospital discharge (whichever occurs first)
- Laboratory testing per site standard practice; if laboratory testing is part of the standard of care and includes CBC and serum creatinine, these should be recorded. The results of any additional tests performed per site standard practice should also be collected.
- Cardiac biomarkers (preferably cTn I or T; if not available, then CKMB is acceptable) should be measured 2 to 6 (up to 12) hours postprocedure. If cardiac biomarkers are elevated and there is a clinical suspicion of myocardial ischemia (for example, due to new ischemic ECG changes [such as ischemic ST changes or new pathological Q waves] or new LBBB, angiographic evidence of a flow-limiting complication, or imaging evidence of new loss of viable myocardium or new regional wall motion abnormality), serial measurements should be taken every 6 to 12 hours until a decline is noted.
- Documentation of any adverse events/ serious adverse events occurring since the point of enrollment. All clinically significant adverse events should be carefully documented by the research staff using the adverse event data forms. In the event of repeat intervention after the index procedure or repeat diagnostic cardiac catheterization (regardless of whether revascularization was performed), procedural angiographic images should be forwarded to the Angiographic Core Laboratory. For all adverse events that represent a potential endpoint event, all relevant medical information (including clinically relevant imaging data, ECG data, and the results of relevant laboratory testing performed as part of the standard of care) should be collected and retained as part of the research file to support adverse event analysis and adjudication.

Prior to hospital discharge, research staff should review the follow-up requirements with the subject to help ensure that he or she returns to the clinic for the 30-day follow-up visit. Telephone numbers should be obtained from the subject to ensure the ability to contact him or her at the required time. These phone numbers should include all home numbers, work numbers and primary physician numbers. A phone number of a relative or friend should also be requested.

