- PCI related MI is arbitrarily defined by elevation of cTn values ( $>5 \times$  99th percentile URL) in patients with normal baseline values ( $\leq$ 99th percentile URL), or a rise of cTn values  $>20\%$  if the baseline values are elevated and are stable or falling, within 48 hours of the procedure.\* In addition, either (i) new ischemic ECG changes (e.g., ischemic ST changes or new pathological Q waves) or new LBBB, or (ii) angiographic findings consistent with a procedural complication (e.g., loss of patency of a side branch, persistent slow-flow or no-reflow, or embolization) or (iii) imaging demonstration of new loss of viable myocardium or new regional wall motion abnormality are required.
- Stent thrombosis associated with MI when detected by coronary angiography or autopsy in the setting of myocardial ischemia and with a rise and/or fall of cardiac biomarker values with at least one value above the 99th percentile URL.
- CABG related MI is arbitrarily defined by elevation of cardiac biomarker values ( $>10 \times$  99th percentile URL) within 48 hours of the procedure in patients with normal baseline biomarker values ( $\leq$ 99th percentile URL).\* In addition, either (i) new pathological Q waves or new LBBB, or (ii) angiographic documented new graft or new native coronary artery occlusion, or (iii) imaging evidence of new loss of viable myocardium or new regional wall motion abnormality are required.

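### Biomarker sampling is required only around the index procedure, and repeat draws need both an elevated first value and clinical suspicion, so some PCI-related MIs are found only if local practice happens to look

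*Protocol*

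**What the plan says.** **Endpoint.** TV-MI is a component of TLF (Protocol 5.3.1). In the MI definition of Protocol Appendix A (17.1), "PCI related MI is arbitrarily defined by elevation of cTn values" above 5 times the 99th percentile URL when baseline is normal, or by a rise of more than 20% "if the baseline values are elevated and are stable or falling, within 48 hours of the procedure". ECG, angiographic or imaging evidence is needed as well. SAP 2.2.3.3 repeats this definition.

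**Required sampling.** Protocol 7.4 and Table 3 footnote 5 say that biomarkers "should be measured 2 to 6 (up to 12) hours postprocedure". Repeat draws carry a double condition: "If cardiac biomarkers are elevated and there is a clinical suspicion of myocardial ischemia", then "serial measurements should be taken every 6 to 12 hours until a decline is noted". Footnote 4 ties the baseline draw to the index procedure. Table 3 has a single post-procedure column, following day 0, for both the biomarkers and the ECG of footnote 2. SAP 2.4.2 lists the same two biomarker collection points.

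**Staged procedures.** Under Protocol 7.3.5, when complications force the index procedure to stop, "staged treatment of a target lesion is permitted provided the staged procedure is performed" more than 72 hours and less than 14 days later. That section mentions neither biomarkers nor an ECG. Footnote 7 adds: "Procedural angiographic images, ECG data, and the results of laboratory testing should be submitted for all repeat revascularizations".

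**Scoring.** A subject with no recorded event and at least 11 months of follow-up enters the primary analysis as a non-event (Protocol 11.4.3; SAP 5.2.1).

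**The concern.** The definition and the measurement schedule do not cover the same ground.

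- **Staged target-lesion PCI.** A staged procedure starts a new 48-hour window in which nothing has to be measured. The missing baseline matters as much as the missing follow-up draw. Without it the CEC may be unable to tell whether the normal-baseline or the elevated-baseline branch of the definition applies.
- **Suspicion with a normal first value.** The protocol's examples of suspicion (ischaemic ECG changes, a flow-limiting angiographic complication, new imaging loss) are nearly the same as the second limb of the MI definition. A subject may already meet that limb, have a normal early value, and have no required second draw.

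An MI missed in either way becomes a non-event in a non-inferiority comparison with a fixed absolute margin. Missed events in both arms shrink the observed difference and so favour the device.

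No planned analysis addresses this. The tipping-point analysis is for subjects with insufficient 12-month follow-up (SAP 4.4). The alternate troponin thresholds (SAP 5.2.2) and the peak-value rule (SAP 5.6.3) use only samples that were drawn.

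**Working it through.** **1. The plan's own figure.** Inputs from Protocol 11.3.1: TLF 6.5% in each arm, margin m = 0.03575, one-sided alpha 0.025, 1034:517. For the Farrington-Manning test,

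power = Φ{[m − (pI − pC) − 1.96·SE0] / SE1},

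where SE0 uses the rates fitted under pI − pC = m and SE1 uses the assumed rates.

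- Fitted rates: 4.575% (control) and 8.150% (intervention).
- SE0 = √(0.04575×0.95425/517 + 0.08150×0.91850/1034) = 0.01252.
- SE1 = √(0.065×0.935×(1/517 + 1/1034)) = 0.01328.
- Power = Φ[(0.03575 − 1.96×0.01252)/0.01328] = Φ(0.844) = 80.06%.

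This reproduces 1551 evaluable subjects at 80% power.

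**2. Window not covered.** If the first value is normal, the last required sample falls at 2 to 12 hours. After a 12-hour draw, 48 − 12 = 36 hours (75%) have no required sample. After a 2-hour draw, 48 − 2 = 46 hours (96%) have none. After a staged procedure all 48 hours have none.

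**3. Staged procedures.** The documents give no staging rate and no procedural MI rate. Assume that 0.5% to 3% of subjects are staged and that 2% to 5% of those have a procedural MI.

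- Staged subjects: 1632 × 0.005 = 8 to 1632 × 0.03 = 49.
- MIs with no required measurement: 1632 × 0.005 × 0.02 = 0.16 to 1632 × 0.03 × 0.05 = 2.4.
- Expected TLF events at 6.5%: 1632 × 0.065 = 106. Losing 2.4 leaves about 97.7% capture.
- Expected TLF events with the true difference at the margin: 1034 × 0.10075 + 517 × 0.065 = 138. Losing 2.4 leaves about 98.3%.

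**4. Normal first value with suspicion.** Suppose the first draw is a fraction q of the 48-hour peak and the peak exceeds 5 times URL. The first value then exceeds 5q times URL. It can be at or below URL only if q is below 1/5 = 20%. This gap therefore concerns late risers only. The documents give no count of them.

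**5. Effect on type I error.** Put the true difference at the margin (6.5% vs 10.075%) and let a fraction s of TLF events be captured in both arms. At s = 0.98 the observed rates are 6.37% and 9.8735%, a difference of 3.5035 points. The formula in step 1 gives SE0 = 0.01418, SE1 = 0.01419 and

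Φ[(0.03575 − 0.035035 − 1.96×0.01418)/0.01419] = Φ(−1.907) = 2.8%.

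| Capture of TLF, both arms | One-sided type I error |
|---|---|
| 100% | 2.5% |
| 99% | 2.7% |
| 98% | 2.8% |
| 95% | 3.4% |
| 90% | 4.6% |

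The assumed staging effect sits near the 98% row. The lower rows are illustrations; nothing in the documents places the trial there.

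**The case against.** Much of the case against a strong reading is sound.

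- **Detection remains possible.** A reader might infer that these MIs cannot be detected. The documents do not support that. Site-practice results and standard-of-care results for potential endpoint events are collected (Protocol 7.4), a re-introduced guiding catheter must be documented as a repeat intervention, films go to the core laboratory, and the CEC reviews all relevant records (10.2). The serial-draw rule is a minimum, and the first draw may be as late as 12 hours. What stands is that submitting a result is not the same as being required to obtain it.
- **The 30-day ECG.** It is mandatory and falls after any staged procedure, so new Q waves could appear on it. It cannot supply a troponin within 48 hours.
- **Wording.** The post-procedure language of 7.4 could be stretched to a staged procedure. Nothing says that the schedule restarts, and footnote 4 names the index procedure.
- **The troponin cut-off.** A reader might infer that an early draw at 30% to 90% of the peak raises the effective cut-off well above 5 times URL. It does not if elevated has its ordinary meaning of above URL. A first value at 30% to 90% of a peak above 5 times URL is itself above 1.5 to 4.5 times URL, so a suspected case would trigger the series.
- **Differences by arm.** Operators are not among the blinded parties (11.5.2), so staging or discretionary sampling could differ by arm. The documents give no evidence that it does, and staging is limited to listed complications. Even if all 2.4 MIs fell in the BuMA arm, the shift would be 2.4/1088 = 0.22 points against a margin of 3.575.
- **Timing.** The synopsis anticipates the last enrolment in August 2019, before protocol version 8.0 of 26 March 2020. On that timeline new wording recovers no past sample. This is why the fix needs a SAP step.

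**Conclusion.** Both gaps are in the text. Followed exactly, the schedule leaves a primary-endpoint component with no required measurement after a staged target-lesion PCI, and with no required repeat draw when ischaemia is suspected but the first value is normal. Ascertainment then rests on local practice, and an undetected MI is counted as freedom from TLF.

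The direction favours non-inferiority and the size is small. Staging accounts for at most about 2.4 missed MIs under assumed rates (3% staged, 5% procedural MI). At about 98% capture in both arms, one-sided type I error is about 2.8% instead of 2.5%. The contribution of late risers is unknown and is confined to first draws below 20% of the peak. The point is worth fixing because it touches the primary endpoint, the error runs towards the claim, and the remedy is cheap. It does not by itself put the trial's conclusion in doubt.

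**What to change.** 1. In Protocol 7.3.5 and Table 3, state that footnotes 2, 4 and 5 (post-procedure ECG, baseline biomarkers, post-procedure biomarkers) apply to any staged target-lesion PCI.
2. In Table 3 footnote 5 and Protocol 7.4, let clinical suspicion of ischaemia alone trigger repeat biomarker draws within the 48-hour endpoint window, whatever the first value. Elevation without suspicion would still need no series.
3. For procedures already done, add to the SAP a table by arm of staged target-lesion procedures and suspected-ischaemia cases without adequate biomarkers. Extend the tipping-point analysis (SAP 4.4 and 5.2.2) to include these subjects as unknown outcomes.

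Items 1 and 2 concern endpoint measurement, not treatment, and help only procedures still to come. Their cost is footnote wording, a few routine draws and ECGs, and occasional repeat draws in subjects already under suspicion. Item 3 costs one table and a wider definition of missing outcome. It is the part that can still help if enrolment closed as anticipated.
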